Participants who are interested in the study will present for their baseline testing prior to initiation of their rTMS treatment course. The testing will occur in a designated research space, likely W264 or T212 in General Hospital. This is estimated to take 1-3 hours, depending on whether or not an MRI is included. These assessments include NIH Toolbox cognitive and emotional batteries (30-45 minutes), Temperament and Character Inventory (30 minutes), MOCA, CGI, PHQ-9 and MADRS (20-30 minutes total), and neurobehavioral testing and neurologic exam (30-60 minutes). Patients will have heart rate variability and facial movements monitored while viewing video clips or images, or hearing stories that may be emotionally charged or neutral (10-15 minutes). EEG will be recorded at rest and during tasks (30 minutes). Some patients may be given an actigraphy wristband to monitor their daily level of activity and their circadian rhythms. Some of these assessments are already obtained as part of the initial work-up for rTMS patients and that data is available for review under a separate previously approved IRB. The neuroimaging will include 21 minutes of resting state fMRI, T1rho, T1 MPRAGE, and DTI (<=60 minutes total). A research team member will escort the patients receiving MRIs to the MRI scanner and back. If a subject chooses to participate in the Vocal Pattern detection portion of the study, they will complete the procedures once weekly for the entirety of their TMS treatment course. The research team member will schedule this with the subject in advance so they are prepared for the length of the visit. Subjects will complete the PHQ9 questionnaire, if they have not already. Next, the recording part will begin with the reading the Grandfather Passage, and the Rainbow Passage. Finally, the subject will be asked some questions about your daily life and your interests.

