The course of TMS will occur as clinically determined by the TMS physicians providing the patient's care. The only unique aspect is that patients in the study will be randomized to either receive rTMS at the F3 location (determined using free software from clinicalresearcher.org) or the 5.5cm method, as is the current standard of clinical care at the University of Iowa for clinical rTMS treatments. Some early internal data has shown that these targets can vary anywhere from a few millimeters apart to a few centimeters, but all targets are within the prefrontal cortex on the left side and consistent with the FDA-approved treatment region for major depressive disorder. The nature of these targeting strategies

should prevent any target from ever falling outside a clinically approved range, but if for some reason it appears that a target is outside of the FDA-approved target region, a study physician will be called to evaluate and confirm the targeting, and adjust if felt to be clinically inappropriate (e.g., not in the prefrontal cortex for that patient). Noninvasive autonomic measures will be obtained during the course of treatment including blood pressure, heart rate, pupil size, and facial movements, although this should not interfere with or delay the administration of the TMS therapy. Some of these measures are already intermittently obtained on patients undergoing TMS therapy.

Treatment will then proceed as managed by the clinical rTMS service at University of Iowa. Follow-up appointments will occur as clinically scheduled by the rTMS clinical service and the patient's other providers as is standard of care. The patient and raters will be blinded to the treatment target for each patient, which will be assigned randomly. The treatment technician will be aware of the treatment site as needed for performing the appropriate measurements and targeting procedure during appointments.

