After a patient has either completed their rTMS course or the course has been terminated by the rTMS team for whatever reason, the patient will have the same testing performed as was performed at their initial study visit. This may include an MRI if patient consented to this and a pre-treatment MRI was conducted on the patient. For purposes of the study, the follow-up MRI could occur either at the very end of the treatment course or at some point during the treatment course, as determined by the study physicians and with patient approval/agreement. They will then be asked to schedule a follow-up phone call 4-6 weeks after completion of the rTMS treatment course, and some questionnaires may be administered over the phone at that time, including a PHQ-9. After this visit, they will no longer be a part of the study.

Recruitment

Patients will be recruited as described above. Only patients who come for and complete a clinical rTMS intake will be asked to participate in the study.

Determination of Treatment-Resistant Depression

Treatment resistant depression will be identified based on clinical interview by a physician with special training in rTMS or psychiatry. This will be a standard clinical interview that will confirm the diagnosis of major depressive disorder, rule out other causes of depression, and evaluate for previous failure of medication and psychotherapy trials. This is standard of care for rTMS treatment as determination of whether it is indicated for use for major depressive disorder, and thus occurs as part of every rTMS evaluation. After this appointment, further questioning may occur by the research study team if needed to confirm that patient meets study criteria or to clarify any information obtained during the clinical interview.

Inclusion Criteria

As per the IRB:

Inclusion:

- Diagnosis of major depressive disorder
- Age greater than or equal to 18 years
- Able to consent for treatment and research participation
- English-speaking
- Have been evaluated by a psychiatrist or neurologist with expertise in TMS and felt to be an appropriate candidate to undergo TMS treatments

Exclusion Criteria

As per the IRB:

Exclusion:

- Age less than 18 years
- Patients that are excluded during TMS assessment including:
- Patients with epilepsy or seizure disorder
- Patients with implanted ferromagnetic equipment in their face or skull near the stimulation target

MRI Exclusion criteria:

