Title: The Effects of Repetitive Transcranial Magnetic Stimulation Prefrontal Target Location on  
Outcomes for Major Depressive Disorder

ID: 201709834

Date: 08/22/2019

rTMS Clinical Database (IRB ID#201709834)  
Data Analysis Plan

We will compare pre- and post-treatment rating scales, cognitive scores, and EEG/MRI results. Rating scales and cognitive/neurobehavioral scores will be analyzed using hypothesis-driven t-tests. iPad cognitive testing is normed to a US population adult control and results will be analyzed as T-statistics comparing the patients against a general population sample. A comparison of mean changes with confidence intervals and standard deviation calculations will be analyzed, as well as the difference in remission and response rates to treatment. For MRI we will compare structural volumetric changes, functional connectivity changes, T1rho pH changes, and DTI anisotropy changes.

Analysis pipeline is well established as mentioned above, with R package RnBeads and Minfi. We will control for standard demographics, including age, sex, race and psychotropic medication use known to affect DNA methylation status.

Audio recordings and their transcription are analyzed using a machine-learning algorithm to evaluate the predictive quality of vocal pattern detection and content value for treatment response to TMS.

Data received from IRB#201810778 will be used a comparison group for this study's heart rate variability data. Mean differences will be compared with t test statistics.

Based on previous work showing small efficacy differences between targets (31% remission with 5cm rule vs. 35% remission with certain Brodmann area targeting), power analysis with desired power of 0.80 and alpha of 0.05, we would need approximately 88 patients (44 in each group). We propose to recruit 200 patients.

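### The supplied documents base power on a between-target remission difference but name no primary F3 versus 5.5cm comparison, no remission definition and no multiplicity rule

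*SAP*

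**What the plan says.** **Design.** Under Study Procedure Timeline and Protocol, the Protocol says that "patients in the study will be randomized to either receive rTMS at the F3 location" or at the target found by the 5.5cm method. Baseline testing includes "MOCA, CGI, PHQ-9 and MADRS (20-30 minutes total". Once the course has ended, by completion or by termination, "the patient will have the same testing performed as was performed at their initial study visit". A phone call four to six weeks later may add another PHQ-9.

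**Analysis.** The first paragraph of the SAP's Data Analysis Plan opens with "We will compare pre- and post-treatment rating scales, cognitive scores, and EEG/MRI results". It assigns t-tests to the rating and cognitive scores, then adds: "A comparison of mean changes with confidence intervals and standard deviation calculations will be analyzed". The same sentence goes on to bring in the two binary outcomes: "as well as the difference in remission and response rates to treatment".

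**Sample size.** The last paragraph of the SAP takes its effect from earlier work, "31% remission with 5cm rule vs. 35% remission with certain Brodmann area targeting". With power 0.80 and alpha 0.05 it concludes that "we would need approximately 88 patients (44 in each group". It then proposes to recruit 200.

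**Absent from both documents:** a primary outcome or test, a scale and cut-off for remission or response, an order of testing, a multiplicity rule, and a window for the post-course assessment.

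**The concern.** Alpha of 0.05 appears only as an input to one power calculation for remission. Nothing says which reported result is that test. Mean change, response and remission can each be computed on MADRS and on PHQ-9, which gives six candidate comparisons at the post-course visit. An analyst could follow the plan exactly and still settle on the deciding measure after seeing all six. A claim that one target is better would then carry more than a 5% chance of being false, and a reader could not tell by how much. Blinding of patients and raters protects the ratings. It does not limit which outcome is chosen at analysis.

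**Working it through.** **1. The plan's own figure.** Inputs from the SAP: p1 = 0.31, p2 = 0.35, power 0.80, alpha 0.05, equal groups. The SAP does not state sidedness; two-sided is assumed. With the pooled two-proportion formula and mean rate 0.33:

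n = [1.960·√(2·0.33·0.67) + 0.842·√(0.31·0.69 + 0.35·0.65)]² / 0.04²
= [1.303 + 0.559]² / 0.0016 ≈ 2,169 per group, or 4,338 in total.

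A one-sided test needs 3,416 in total. Continuity-corrected, unpooled and arcsine versions do not come near 88 either. For comparison, 44 per group fits a two-sided comparison of means at √(2/44)·(1.960 + 0.842) ≈ 0.60 SD, but the documents state no such effect.

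**2. Power for 31% versus 35%, two-sided 0.05**

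| Per arm | Either direction significant | Correct direction only |
|---|---|---|
| 44 | 6.8% | 5.9% |
| 100 | 9.2% | 8.7% |

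At 100 per arm (200 split equally), 80% power is reached at about 31% versus 50%. For a mean score it is reached at about 0.40 SD unadjusted. With baseline adjustment and an assumed baseline correlation of 0.5, it is 0.398·√(1 − 0.5²) ≈ 0.34 SD.

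**3. What the documents fix and leave open**

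| Element | In the documents | Still open |
|---|---|---|
| Contrast | Two randomised targets; two-group power statement | Which outcomes are compared by target |
| Measure | Mean change, response and remission all listed | Which one decides |
| Scale | MADRS and PHQ-9 both collected | Which one defines remission and response, and the cut-offs |
| Visit | Pre/post wording points to the post-course testing | Its window, and an explicit tie to remission |

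**4. False-positive chance.** If the tests were independent, the chance of at least one p<0.05 would be 1 − 0.95² = 9.75% for two tests and 1 − 0.95⁶ = 26.5% for six. The tests are correlated, so they were simulated: 20,000 trials per setting with no true difference, 100 per arm, and normal outcomes on two scales correlated 0.5, 0.65 or 0.8. Remission was 31% (the SAP's figure) and response 55% (assumed; 45% and 65% also tried). Each trial used a t-test on change and pooled z-tests on the rates. The correlation between change and the variable underlying remission was set to 1.0 or 0.8.

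| Tests available | Chance of at least one p<0.05 |
|---|---|
| 1: remission on one named scale | 5.0-5.3% |
| 2: remission on either scale | 8.9-9.8% |
| 3: mean change, response, remission on one scale | 10.6-11.8% |
| 6: those three on both scales | 17.5-20.9% |

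At 44 per arm the six-test figure is 17.2-20.2%. A separate simulation, with remission and response both cut from the same score, gave about 17% for six tests at a correlation of 0.9. No CGI or follow-up-call tests are counted here. Adding three PHQ-9 tests at the call gave about 21-26% over correlations of 0.5 to 0.9.

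**The case against.** **The SAP never says these outcomes are compared by target.** This is correct. Its sentence on scales is worded pre/post, the document is headed as a clinical database, and the rates in the power statement are for a 5cm rule and a Brodmann-area target, not the trial's own two methods. The between-target reading is an inference. It rests on the randomisation and on a two-group calculation at alpha 0.05, and without it the plan would contain no analysis of its randomised question. The inference is sound, but it limits confidence.

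**The visit is given.** A reader might infer that no assessment time is specified at all. The documents do not support that: the pre/post wording, with the Protocol's repeat testing, points to the post-course visit. Only PHQ-9 is named for the later call, and only as a possibility. What stands is the missing window and the missing explicit link to remission.

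**The power statement makes remission primary.** It does not say so. Even on that reading the scale and cut-off remain open, and the two-scale choice alone gives 9-10%.

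**The text may be incomplete.** The SAP's methylation paragraph refers back to earlier material that the SAP does not contain. A primary outcome could be stated elsewhere, so the point is limited to the supplied documents.

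**The work may be exploratory.** If so, family-wise error matters less, but a plan that states an alpha, a power and a required number should say that it is exploratory.

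**Conclusion.** The point holds, at medium confidence, as a change the sponsor should make. In the supplied documents no primary target comparison is named, remission has no scale or cut-off, and no rule governs multiple tests. The illustrative cost is a false-positive chance of about 9-10% for remission on either scale and about 18-21% for six tests, against 5% for one. This rests on the assumed test count, on correlations of 0.5 to 0.8 (slightly lower at 0.9) and on the assumed response rate. None of these assumptions comes from the documents.

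Two stronger readings should be resisted. A reader might infer that the trial really is sized on remission. Remission is only the stated rationale, because 88 does not follow from 31% versus 35%. That is a separate defect, and it matters here only because the primary test and its power basis must be set together. A reader might also infer that the result has been, or will be, selected after the fact. The documents show only that the plan would not prevent it.

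**What to change.** Before any analysis by assigned target, amend the SAP as follows.

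- **Primary.** Name one F3 versus 5.5cm test at two-sided 0.05. The preferred choice is the post-course MADRS score compared between randomised targets with adjustment for baseline MADRS, in all randomised patients as assigned. MADRS is already collected at baseline and repeated after the course. Unlike PHQ-9, it is not named for the later call, so this choice also settles the visit. State an assessment window that also covers patients whose course ends early.
- **Secondary.** Define remission and response on one stated scale with stated cut-offs. Label everything else secondary or exploratory, and say for each outcome whether it compares targets, pre with post, or patients with an outside group.
- **Multiplicity.** Test confirmatory secondary claims only if the primary is significant, for example with Holm. In the simulation, Holm on the other five tests without that gate gave an overall error of about 7-8%. With the gate it stayed at about 5%.
- **Power basis.** Restate it for the planned 200 without enrolling more. Give the detectable difference (about 0.40 SD unadjusted, or about 0.34 SD at an assumed baseline correlation of 0.5) and acknowledge that 31% versus 35% is out of reach. The documents give no MADRS SD or target effect, so the sponsor must supply both.

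The cost is SAP wording, a less favourable power statement, and no confirmatory secondary claims if the primary fails. No procedure or patient is added.

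### Heart rate variability is compared with another study's data by an unadjusted t-test; a regression adjusted for age and sex, reported as observational, would be a cheap improvement

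*SAP*

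**What the plan says.** The SAP's Data Analysis Plan gives the HRV analysis in two sentences. The first brings in the comparator: "Data received from IRB#201810778 will be used a comparison group". The second gives the method: "Mean differences will be compared with t test statistics". Neither mentions covariates, matching, weighting or the observational nature of the comparison.

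Four other places bear on the point:

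- **Randomisation.** The Protocol's description of the TMS course says that "patients in the study will be randomized to either receive rTMS at the F3 location" or by the 5.5 cm method. Nothing else is randomised.
- **Covariate adjustment.** The SAP's only adjustment sentence is in the methylation paragraph: "We will control for standard demographics, including age, sex, race and psychotropic medication use known to affect DNA methylation status".
- **Timing of HRV.** Under the Protocol's baseline testing, participants "will present for their baseline testing prior to initiation of their rTMS treatment course", and the assessments include HRV: "Patients will have heart rate variability and facial movements monitored while viewing video clips or images, or hearing stories". After the course, "the patient will have the same testing performed as was performed at their initial study visit".
- **Pre/post analysis.** The SAP's opening sentence, "We will compare pre- and post-treatment rating scales, cognitive scores, and EEG/MRI results", does not list HRV.

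**The concern.** This is a comparison between participants of two different studies. Randomising patients between two targets balances the target groups against each other. It does nothing to balance this study's patients against participants enrolled elsewhere. A plain t-test attributes the whole difference in means to group membership. If the two groups differ in age or sex, and HRV varies with these, part or all of that difference may have nothing to do with group.

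The value to be compared is also open. HRV is recorded before rTMS and the testing is repeated afterwards, so the mean differences could be of baseline, post-treatment or change values. Post-treatment values would mix any effect of rTMS into the group difference. Change values would be less exposed to confounding, because stable differences in level largely cancel.

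What is at stake is the reading of one ancillary result, not the trial's main question.

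**Working it through.** The documents give no HRV effect size, SD, sample size or power, so there is no figure of the plan's own to reproduce. The check is therefore an illustration for age. An imbalance in sex acts in the same way.

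**Inputs, all assumed**

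- Age SD 15 years; age gap between the groups 0 or 5 years.
- Correlation of age with HRV, r: 0.1 to 0.5.
- n = 100 or 200 patients with HRV. The 200 is the SAP's overall recruitment target, not a stated HRV sample size.
- m = 50 or 100 comparators.
- No true group effect; baseline or post-treatment values; two-sided 5% test.

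**False-positive rate of the t-test**

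- Spurious difference in SD units: d = r × (5/15).
- Standard error in SD units: √(1/n + 1/m).
- Noncentrality: ncp = d / √(1/n + 1/m).
- Rejection rate: P(|Z + ncp| > 1.96).

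The standard error is √(1/100 + 1/50) = 0.173 at the smallest sizes and √(1/200 + 1/100) = 0.122 at the largest.

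| r | d | rate at n=100, m=50 | rate at n=200, m=100 |
|---|---|---|---|
| 0.1 | 0.033 | 5.4% | 5.9% |
| 0.2 | 0.067 | 6.7% | 8.5% |
| 0.3 | 0.100 | 8.9% | 12.9% |
| 0.5 | 0.167 | 16.1% | 27.5% |

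For example, at r = 0.5 and the largest sizes, ncp = 0.167/0.122 = 1.36, which gives 27.5%. With no age gap, d = 0 and the rate is 5%.

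**Does adjustment correct it?** A separate simulation (4,000 runs, 200 versus 50, r = 0.3, age gap of 0.5 SD) gave 16% for the t-test and 5% for a linear model with group, age and sex.

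**Cost in precision at the 5-year gap**

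- Ratio of adjusted to unadjusted standard error: √((1 − r²)/(1 − R²)).
- R² is the squared correlation of age with group: pq(5/15)² / (1 + pq(5/15)²), with p = n/(n+m) and q = 1 − p.
- Lowest ratio, at r = 0.5, n = 200, m = 50: pq = 0.16, R² = 0.0175, ratio = √(0.75/0.9825) = 0.874.
- Highest ratio, at r = 0.1, n = m = 100: pq = 0.25, R² = 0.0270, ratio = √(0.99/0.9730) = 1.009.

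So the adjusted standard error runs from 13% smaller to 1% larger.

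**What adjustment does not remove.** Suppose the groups also differ by 0.2 SD for an unmeasured reason, such as recording conditions. Then ncp = 0.2 / (ratio × √(1/n + 1/m)).

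- At r = 0.1, n = 100, m = 50: 0.2/(1.007 × 0.173) = 1.15, so the age-adjusted model rejects in 21% of studies.
- At r = 0.5, n = 200, m = 100: 0.2/(0.877 × 0.122) = 1.86, so it rejects in 46%.

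**The case against.** The strongest reply is that no error is shown. The documents do not describe the comparator. It may be similar in age and sex, or even matched, and whether HRV varies with age or sex is not established in them either. Every input to the illustration is assumed. With smaller groups, for example 25 versus 25 or 44 versus 25, the same 5-year gap gives only 5.2% to 6.8% at correlations of 0.1 to 0.3. It is true that nothing in the documents favours one part of the range over another.

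A second reply is that the SAP promises only to compare means. If ages differ and HRV depends on age, the means really do differ, and a t-test that detects this is correct as description. That holds for a purely descriptive reading. But a comparison group is used to say something about group, and a difference confounded by age or sex cannot be attributed to group.

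Third, the remedy is partial and conditional. It leaves unmeasured differences in place, and the documents do not show that age and sex come with the data received. Both limits stand. They are the reasons for the observational label and for a fallback. Change values, if intended, would also reduce the problem, which is a further reason to name the value compared.

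**Conclusion.** The concern holds. The SAP compares two non-randomised groups by a t-test with no stated adjustment, and its one adjustment sentence is tied to DNA methylation. The harm runs from negligible to material: the illustrated false-positive rate is 5% with no age gap and 5.4% to 27.5% with a 5-year gap, depending on the correlation and group sizes. These figures rest wholly on assumed inputs and apply to baseline or post-treatment values. An imbalance is possible but not demonstrated.

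The case for changing the plan is that, under the same assumptions, adjustment costs at most about 1% in standard error and protects against a bias that the SAP gives no ground to rule out. This is a worthwhile improvement to an ancillary analysis. Confidence is medium, because the comparator is undescribed.

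**What to change.** Replace the t-test sentence in the HRV paragraph with:

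> Baseline heart rate variability will be compared with the IRB#201810778 group by linear regression on group, adjusted for age and sex, with psychotropic medication as a sensitivity analysis where it is recorded in both studies and overlaps between groups; the result will be reported as an observational comparison.

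Baseline is proposed because it precedes rTMS, so a treatment effect is not mixed into the group difference. If the sponsor intends post-treatment or change values, those should be named instead.

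The cost is one SAP sentence and a short regression, provided that age and sex can be obtained from IRB#201810778. If they cannot, the comparison should be reported as unadjusted and observational. Naming the time point and adding the label need no further data.

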Targeting either the F3 left prefrontal cortex location or the 5.5cm target location will occur as described above. Targeting the F3 location requires taking measurements of the head circumference, tragus-to-tragus distance, and nasion-to-inion distance, and using computer software to calculate the correct prefrontal target using head landmarks. The 5.5cm target location is determined by measuring 5.5cm anterior to the primary motor cortex of the brain, which is identified using a TMS procedure called motor threshold testing, all of which is done as part of the standard of care in clinical rTMS and will not be altered for this study. Targets will be marked onto a swim cap which the patient will wear during treatments, to ensure that the same target can be stimulated from treatment-to-treatment reliably, again, as is standard practice in rTMS treatments.

Treatment as Usual (Parameters)

Treatment parameters other than stimulation location will be as per clinical standard of care, including 3000 total pulses at a frequency of 10Hz, with 4-second train duration, 26-second off time, for 75 total trains. All treatments will be targeted at the left prefrontal cortex as is FDA-approved for major depressive disorder, and all treatment targets will fall within this region.

Safety

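### The SAP's 0.80 power with 88 patients is not delivered: on its own borrowed remission rates, power is about 6-7% at 44 per group and about 9% at 100 per group

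*SAP*

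**What the plan says.** The SAP (Data Analysis Plan, final paragraph) justifies the sample size in two sentences. The planning effect is "31% remission with 5cm rule vs. 35% remission with certain Brodmann area targeting", introduced with the words "Based on previous work showing small efficacy differences between targets". From a "power analysis with desired power of 0.80 and alpha of 0.05" it arrives at about 88 patients, 44 per group. It then proposes to recruit 200, without linking that number to the 88 and without giving a dropout rate. It does not say whether the test is one- or two-sided.

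The Protocol (Study Procedure Timeline and Protocol) describes different arms. Patients are "randomized to either receive rTMS at the F3 location" "or the 5.5cm method, as is the current standard of clinical care at the University of Iowa for clinical rTMS treatments". The Targeting section defines both. For one arm, "Targeting the F3 location requires taking measurements of the head circumference, tragus-to-tragus distance, and nasion-to-inion distance", which are then entered into software. For the other, "The 5.5cm target location is determined by measuring 5.5cm anterior to the primary motor cortex of the brain".

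Neither document gives a remission rate for F3 or for the 5.5cm method.

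**The concern.** Two things look wrong in the same sentence.

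- **Source of the rates.** They belong to the 5cm rule and to Brodmann-area targeting. Target location is the randomised variable here, so using rates from other targeting methods needs a reason, and none is given.
- **Size of the sample.** A 4-point difference in remission is far too small to be detected with 44 patients per group. The 88 does not follow from the rates placed beside it.

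The power statement is the only account the plan gives of what the trial can show. If it stands, a non-significant F3 versus 5.5cm result would look like an adequately powered negative. In fact the trial would have had little chance of detecting the difference it was said to be planned for.

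**Working it through.** **Inputs.** From the SAP: p1 = 0.31, p2 = 0.35, alpha = 0.05, power = 0.80, 44 per group, 200 recruited. Assumptions: a two-sided test, and 100 per group from 1:1 allocation of the 200.

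**1. Does 88 follow from the SAP's inputs?** For two proportions with pooled null variance,

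n per group = [1.96 × √(2·p̄(1−p̄)) + 0.8416 × √(p1(1−p1) + p2(1−p2))]² / (p2 − p1)²

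- p̄ = 0.33, so 2·p̄(1−p̄) = 0.4422, square root 0.6650.
- p1(1−p1) + p2(1−p2) = 0.2139 + 0.2275 = 0.4414, square root 0.6644.
- n = (1.8625 / 0.04)² = 2,168.05, rounded up to 2,169 per group, or 4,338 in total.

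Other methods do not recover 44 per group:

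| Method | Two-sided | One-sided |
|---|---|---|
| Pooled z test | 2,169 | 1,708 |
| With continuity correction | 2,218 | 1,758 |
| Unpooled variance | 2,166 | 1,706 |
| Arcsine | 2,168 | 1,708 |
| One sample against a fixed 31% (total n) | 1,070 | 845 |

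The stated figure is not reproduced by any of them.

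**2. Power at the stated and planned sizes, 31% versus 35%.** With SE0 = √(0.4422/n) and SE1 = √(0.4414/n), the chance of significance in the expected direction is Φ[(0.04 − 1.96·SE0)/SE1]. Counting rejections in the wrong direction as well adds Φ[(−0.04 − 1.96·SE0)/SE1].

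- n = 44: SE0 = 0.1002, SE1 = 0.1002; Φ(−1.562) = 0.059; with both tails, 0.059 + 0.009 = 0.068.
- n = 100: SE0 = 0.0665, SE1 = 0.0664; Φ(−1.360) = 0.087; with both tails, 0.087 + 0.005 = 0.092.
- One-sided, the figures are 0.106 at 44 and 0.148 at 100.

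**3. What difference would give 0.80?** Against 31%, the other arm would need about 60% remission at 44 per group and about 50% at 100 per group. Those are gaps of about 29 and 19 points, against the 4 points in the SAP.

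**4. What the trial can deliver.** The 95% confidence interval half-width for a difference in remission is 1.96 × √[(p1(1−p1) + p2(1−p2))/n].

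- At 31% and 35%: 1.96 × √(0.4414/100) = 0.130 with 100 per group; 1.96 × √(0.4414/44) = 0.196 with 44.
- At one third in both arms: 1.96 × √(0.4444/100) = 0.131.
- Sensitivity with 100 per group: 25% in both arms gives 1.96 × √(0.375/100) = 0.120; 50% in both arms, the widest case, gives 1.96 × √(0.5/100) = 0.139.
- If, for illustration, only 80 per group were analysed, one third in both arms gives 1.96 × √(0.4444/80) = 0.146.

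The interval is about 13 points either side, and this depends little on which rates are assumed.

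**The case against.** **Borrowed rates are ordinary planning.** Power depends on the assumed rates, the sample size and alpha, not on the names of the methods that supplied the rates. The SAP applies its rates to this trial's own two groups, and when no direct rates exist, related methods are a usual source. This stands. A reader might infer that the stated power does not refer to F3 versus 5.5cm at all. The documents do not support that: it refers to this contrast, on an assumption that is not justified. Nor do they show how far the methods differ. The SAP does not define the 5cm rule or say which Brodmann areas are meant, and a nominal half-centimetre is not shown to change remission.

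**A reader might also infer that power drops steeply if the 5.5cm method already recovers part of the 4-point gap.** That would hold only in a trial of about 4,338 patients. With F3 kept at 35% and the control assumed to be 33%, power goes from 6.8% to 5.4% at 44 per group and from 9.2% to 6.0% at 100, because there is little to lose. With no rate given for either arm, the true gap could as well be larger than 4 points.

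**The 88 may belong to another endpoint.** The SAP names no primary endpoint and lists t-tests on scales beside remission. By the normal approximation, 44 per group gives 0.80 power for a standardised mean difference of about 0.60. That may be where the number came from, but the SAP does not say so; it ties the 88 to remission.

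**The replacement interval has its own assumptions.** It needs a remission level and complete follow-up, while the Protocol expects some courses to end early. Both points are fair, and the proposed wording states them.

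**Conclusion.** The point holds as a wrong stated figure. On the SAP's own rates, two-sided power is about 6-7% with 88 patients and about 9% with 200, not 0.80; about 2,169 per group would be needed. No one-sided or alternative formula tried comes near 44 per group. The lack of any reason for applying 5cm-rule and Brodmann-area rates to F3 versus 5.5cm is a second, lesser gap: an unsupported assumption, not proof that the rates are wrong. Supplying a reason would not rescue the power claim.

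The power figures rest on a two-sided test at 0.05 and, for 200 patients, on equal allocation with everyone analysed. The half-width of about 13 points (about 20 with 88 patients) rests on remission near one third, which is an assumption because the documents give no rate for either arm.

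**What to change.** In the final paragraph of the SAP, with no change in enrolment:

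1. Withdraw the statement that 88 patients give 0.80 power.
2. Say that 31% and 35% are borrowed from the 5cm rule and Brodmann-area targeting and are not rates for either randomised arm.
3. State the precision of the randomised contrast, for example: *If all 200 patients are analysed (100 per arm) and remission is near one third (an assumption), the 95% confidence interval for the F3 minus 5.5cm remission difference is about ±13 percentage points; it is wider if patients are lost.*

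If a control rate is wanted, the site's own 5.5cm patients are a natural source, since the Protocol describes that method as its current standard.

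The cost is SAP wording only. The downside is that a wide interval replaces a claim of 0.80 power, so the plan looks less favourable. The change does not name a primary endpoint or explain how 200 was chosen; those gaps remain.
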